### **11.5.2. Vital Signs and Laboratory Parameters**

The analysis of vital signs and laboratory parameters will include descriptive statistics for the change from Baseline to the endpoint visit, change from Baseline for each visit (vital signs only). Where appropriate, analyses will also include shifts from Baseline to the endpoint visit. For laboratory values, the normal ranges will be used to determine the classifications. Values below the normal range will be classified as low, values above the normal range will be classified as high, and values within the normal range will be classified as normal.

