The current study (313-201901) is the first clinical study of intratympanic OTO-313 in subjects with tinnitus and is composed of 2 parts. Part A is a randomized, double-blind, placebo-controlled cohort to evaluate the safety, tolerability, and plasma pharmacokinetics (PK) of 0.11 mg OTO-313, following intratympanic administration, in subjects with subjective unilateral or bilateral tinnitus. If acceptable safety and tolerability is observed for 8 days in Part A, as determined by the Safety Review Committee, Part B will be initiated. Part B is a randomized, double-blind, placebo-controlled study to investigate the safety, plasma PK, and preliminary efficacy of 0.32 mg OTO-313 in subjects with subjective unilateral tinnitus. If acceptable safety and tolerability is observed for 8 days in the first 12 subjects in Part B, as determined by the Safety Review Committee, the remaining subjects in Part B will be enrolled. The 0.11 mg and 0.32 mg doses of OTO-313 to be tested in this study are expected to be safe and well-tolerated based on preclinical studies and on the clinical Study 311-201501 conducted with OTO-311 in healthy subjects. Preclinical data suggest that the two dose levels of OTO-313 will produce sufficient inner ear exposures of gacyclidine in humans. In addition, the lipid formulation of OTO-313 is expected to maintain sustained exposures to the cochlea over time (at least 7 to 14 days in preclinical testing). Taken together, the preclinical and clinical data support the evaluation of the two dose levels of OTO-313 in this Phase 1/2 study in subjects with tinnitus.

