## **6.2. Compliance**

OTO-313 or placebo will be administered by a physician as a single, intratympanic injection at Day 1. Any deviations in administration will be documented in the source documents and the eCRF.

The site will maintain a log of all investigational product dispensed and returned. Investigational product supplies for each subject will be inventoried and accounted for in the study.

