### **8.7.2. Clinical Laboratory Tests**

All clinical laboratory tests (except for urine pregnancy) will be processed by a Central Laboratory.

Blood and urine samples for hematology, serum chemistry, urinalysis, and pregnancy tests will be prepared using standard procedures.

For Part A, clinical laboratory testing will be completed at Screening, Day 1 (pre-dose), Day 8, and Day 29. In addition, female subjects of childbearing potential will have serum pregnancy test at Screening and a urine pregnancy test at Day 1 (pre-dose) and Day 29. The urine pregnancy tests will be performed locally at the site, so results are available that day.

For Part B, clinical laboratory testing will be completed at Screening, Day 1 (pre-dose), Day 8, and Day 57. In addition, female subjects of childbearing potential will have serum pregnancy test at Screening and a urine pregnancy test at Day 1 (pre-dose) and Day 57. The urine pregnancy tests will be performed locally at the site, so results are available that day.

The blood and urine samples will be used for the following tests:

Hematology: hemoglobin, hematocrit, red blood cell count, white blood cell count with differential, mean corpuscular volume, mean corpuscular hemoglobin, mean corpuscular hemoglobin concentration, and platelet count.

Serum chemistry: albumin, alkaline phosphatase, alanine aminotransferase, aspartate aminotransferase, gamma glutamyl-transpeptidase, bicarbonate, blood urea nitrogen, calcium, chloride, creatinine, glucose, lactate dehydrogenase, phosphorus, potassium, sodium, total bilirubin, and total protein.

Urinalysis: appearance, color, pH, specific gravity, protein, glucose, ketones, nitrite, leukocyte esterase, urobilinogen, and microscopic sediment examination.

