### **11.4.4. Safety Endpoints – Part B**

The safety endpoints for Part B are:

- Type and incidence of treatment-emergent adverse events (TEAEs).
- Clinically significant adverse change from Baseline in audiometry assessments, tympanometry, and otoscopic examinations.
- Clinically significant adverse change from Baseline in clinical laboratory measurements (hematology, serum chemistry, and urinalysis) and vital signs measurements (systolic and diastolic blood pressure, pulse rate).
- Assessment of suicidality via the C-SSRS.

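### For completers, the Day 8 laboratory sample, the one closest to dosing, enters no specified change-from-Baseline or shift summary by treatment group.

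*Combined protocol and SAP*

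**What the plan says.** Section 11.5.2 covers vital signs and laboratory parameters together. It plans "descriptive statistics for the change from Baseline to the endpoint visit, change from Baseline for each visit (vital signs only"), and continues: "Where appropriate, analyses will also include shifts from Baseline to the endpoint visit". By-visit change is thus kept for vital signs, and the only visit named for laboratory change or laboratory shifts is the endpoint visit, which is not defined.

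Section 8.7.2 sets the sampling. "For Part A, clinical laboratory testing will be completed at Screening, Day 1 (pre-dose), Day 8, and Day 29". "For Part B, clinical laboratory testing will be completed at Screening, Day 1 (pre-dose), Day 8, and Day 57". Tables 1 and 2 agree with this.

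Safety and tolerability are the primary objective of both Parts (Sections 2.1.1 and 2.2.1). Sections 11.4.1 and 11.4.4 both list laboratory change as a safety endpoint; the Part B entry begins "Clinically significant adverse change from Baseline in clinical laboratory measurements". Neither names a visit, a criterion or a table.

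**The concern.** Treatment is one injection, so a laboratory effect of dosing could appear early and then reverse. If it did, the Day 8 sample would be the scheduled one best placed to show it. Section 11.5.2 is not silent on this sample. Its parenthesis takes laboratory values out of the by-visit change summary, and its shift sentence does not bring Day 8 back.

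The treatment-group comparison of laboratory safety would then rest on the later sample alone. A modest group difference in a chemistry value at Day 8, too small to be reported as an adverse event and gone by the final visit, would appear in none of the specified tables. No reason is given for handling laboratory values more narrowly than the other safety measures.

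**Working it through.** The plan states no figure to reproduce on this point. The check compares the sampling schedule with the visits that the analysis section names.

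**Step 1: dosing day.** Section 6.2: "OTO-313 or placebo will be administered by a physician as a single, intratympanic injection at Day 1". Days after dosing = nominal visit day − 1.

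**Step 2: post-dose laboratory visits (Section 8.7.2, Tables 1 and 2) against the visits named in Section 11.5.2**, reading endpoint visit as the end-of-study visit:

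| Part | Post-dose laboratory visit | Days after dose | Change from Baseline specified | Shift specified |
|---|---|---|---|---|
| A | Day 8 | 8 − 1 = 7 | No | No |
| A | Day 29 | 29 − 1 = 28 | Yes | Yes |
| B | Day 8 | 8 − 1 = 7 | No | No |
| B | Day 57 | 57 − 1 = 56 | Yes | Yes |

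In each Part, 1 of the 2 scheduled post-dose samples is left out, and it is the earlier one.

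**Step 3: sensitivity to the undefined term.** If endpoint visit means the last available value, Day 8 enters for a subject with no later sample. A completer has a later sample by definition, so the result for completers does not change.

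**Step 4: how the other safety measures are handled.**

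- Vital signs (11.5.2): change at each visit.
- Otoscopy (11.5.3): classification by visit; change in classification only to the endpoint visit.
- Audiometry (11.5.4): thresholds by visit.
- Tympanometry (11.5.5): shifts to every post-Baseline visit.
- C-SSRS (11.5.6): tabulated for each visit.

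Otoscopy shares the endpoint-visit limit on change, but its findings are still tabulated at every visit. Laboratory data are the only one of these measures with no specified tabulation at an intermediate visit.

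**Step 5: reach of the Safety Review Committee.** The committee reviews laboratory data through Day 8 for Part A and for the first 12 subjects dosed in Part B, blinded at first (Synopsis, Section 14.6.1). If the dose is not changed and 50 subjects are randomised in Part B, 50 − 12 = 38 fall outside that review, and 38/50 = 76%.

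**The case against.** The strongest reply is that Day 8 laboratory data are not lost. Much of it stands:

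- The laboratory safety endpoint carries no visit limit, so a clinically significant change at Day 8 falls within it.
- Under Section 9.1 a laboratory abnormality is an adverse event if it leads to discontinuation, treatment or further diagnostic work-up, or accompanies signs or symptoms of significant clinical impact. Section 11.5.1 tabulates such events by preferred term and system organ class, with severity and relationship, whenever they arise.
- The Safety Review Committee may unblind individual subjects.
- Section 11.5 promises descriptive tabulations for the safety set, and the wording of 11.5.2 does not forbid further tables.
- The analysis is descriptive, so a Day 8 table could be added later with no type I error cost.

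A reader might therefore infer that Day 8 data enter no safety summary at all. The documents do not support that. The gap is narrower: no specified by-visit laboratory change or shift table by treatment group. The routes above do not fill it. A subclinical group shift may meet none of the adverse event conditions. The committee's review covers part of the sample and is not planned as a comparison of arms. The laboratory endpoint has no table attached. The protocol defers some matters to a SAP (missing data and TFI scoring in 11.6, lead-in C-SSRS events in 11.5.1), but not laboratory tables, and the text supplied contains no separate laboratory specification.

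Two further inferences are tempting and should not be made. One is that Day 8 is the only laboratory sample inside the expected exposure period. The phrase in Section 1.1, "at least 7 to 14 days in preclinical testing", concerns exposure of the cochlea and sets a lower bound. It says nothing about systemic exposure, which is what liver enzymes or creatinine would reflect, and Section 1 expects intratympanic delivery to give less systemic exposure. The other is that an abnormality at Day 8 would have returned to normal by Day 29 or Day 57. The documents give no time course for any laboratory effect, so no residual fraction can be calculated and the content of the final shift table cannot be predicted.

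**Conclusion.** The point holds in its limited form. Followed as written, Section 11.5.2 leaves 1 of the 2 scheduled post-dose laboratory samples per completer, the one 7 days after dosing, out of every specified laboratory change and shift summary by treatment group. This applies in both Parts.

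The conclusion rests on two readings: that endpoint visit means the end-of-study visit (or, for completers, the last value), and that the parenthesis in 11.5.2 restricts the by-visit summary as it says. It does not rest on any assumed rate of recovery.

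What could go unseen is an early, reversible, subclinical laboratory change. The documents give no basis for judging how likely one is. This is a shortfall in the specified tables, not a failure to collect or monitor safety data. It deserves correction because safety is the primary objective and laboratory change is a named endpoint.

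**What to change.** In Section 11.5.2:

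1. Delete the parenthesis that limits by-visit change to vital signs.
2. State that laboratory change from Baseline, and low/normal/high shifts from Baseline, will be summarised by treatment group at Day 8 and at the endpoint visit, in each Part.
3. Define endpoint visit, including which value is used for a subject who terminates early.

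A shift from Baseline to the worst post-dose value is optional; with two scheduled post-dose samples it adds little once both visits are tabulated.

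The cost is a short text change and a few more descriptive tables from data already collected, with no added visits, samples or subjects.

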### **11.5.3. Otosopic Examinations**

Observations recorded during the conduct of otoscopic exams will be descriptive in nature. The number and percent of subjects presenting with each Otosopic classification will be provided by treatment group and study visit. Where relevant, the number and proportion of subjects with changes in their otoscopic classification from Baseline to the endpoint visit will also be provided for each treatment group.

### **11.5.4. Audiometry Assessments**

Descriptive summary statistics for audiometric assessments of air and bone conduction thresholds at each frequency will be provided by treatment group and study visit.

All audiometry assessments will be tabulated separately for the treated and untreated ear.

### **11.5.5. Tympanometry**

Shift tables representing the proportion of subjects with changes in their tympanogram from Baseline to each post-Baseline study visit will be calculated for each treatment group.

Tympanogram changes will include both the type of tympanogram (A, B-small volume and/or normal, B-large volume, or C), as well as, whether the tympanogram was judged to be normal or abnormal.

### **11.5.6. Columbia-Suicide Severity Rating Scale (C-SSRS)**

The C-SSRS will be administered at each visit using the appropriate version i.e. “Baseline” or “Since Last Visit”.

The “Baseline” version of the C-SSRS captures both suicidal ideation and suicide behavior (lifetime). There are 5 suicidal ideation questions, each captured as yes/no for the subject’s lifetime. There are 4 suicidal behavior questions, each captured as yes/no for the subject’s lifetime. An additional question asks if suicidal behavior is present during the visit. All suicidal ideation and behavioral variables as outlined here will be tabulated overall and by treatment group.

The C-SSRS version used at visits subsequent to the Baseline Visit will be a modified version of the “Baseline” C-SSRS. This “Since Last Visit” version uses the same individual variables for suicidal ideation and behavior assessed at Baseline to capture changes, if any, from previous assessments. In addition, overall suicidality (yes/no) will be defined as any suicidal ideation or behavior since the last visit. All suicidal ideation and behavior variables will be tabulated overall and by treatment group for each study visit. All C-SSRS data will be included in data listings.

### **11.6. Handling of Missing Data, Subject Withdrawals, and Treatment Failures**

The SAP will include details regarding the handling of missing data as well as the instructions for scoring the TFI, including handling of missing TFI questionnaire items. Every reasonable effort will be made to encourage compliance with study measurement methods and study procedures to minimize missing data.

Every reasonable effort will be made to follow subjects who withdraw from the study for safety evaluation until the date they would have completed participation.

### **11.7. Interim Analyses**

There are no formal interim analyses planned. Blinded reviews of safety data will be conducted as described in [Section 14.6](#); however, the review of such data is not intended to impact the study conduct unless there are safety concerns. As such, it is expected that the study will continue to its scheduled completion barring any unexpected safety issues.

## **12. INVESTIGATIONAL PRODUCT INFORMATION**

### **12.1. Physical Description of Investigational Product**

The investigational product administered to subjects will be OTO-313 and placebo. OTO-313 is supplied as a 1 mL sterile solution (1.6 mg/mL [0.16%] gacyclidine in medium-chain triglycerides) in a vial. Placebo is provided as 1 mL of sterile 100% medium-chain triglycerides solution in a vial. The vials are provided as kits, and all kits must be stored at 2-8°C until use.

## **12.2. Directions for Use**

OTO-313 and placebo syringes will be prepared in a clean, secure location at room temperature. Please refer to the Pharmacy Manual for detailed investigational product preparation instructions.

## **12.3. Packaging and Labeling**

### **12.3.1. Packaging**

All investigational product kits will be labeled with information that will meet the applicable regulatory requirements.

### **12.3.2. Labels and Labeling Instructions**

A label will be affixed to each kit box indicating kit number and storage instructions. A label will be affixed to the OTO-313 and placebo vials indicating contents and storage instructions.

## **12.4. Management of Clinical Supplies**

The clinical supplies will be managed by WebEZ randomization system. WebEZ will create shipment requests that will be generated based on inventory thresholds that are set for each site. A shipment request will be generated by WebEZ and sent to the clinical supply vendor (Almac). Upon shipment and receipt of the clinical study material, the site personnel will acknowledge the shipment and identify any damaged, missing, or unusable kits so they will not be dispensed.

### **12.4.1. Storage of Kits**

All kits will be stored at 2-8°C, with allowable temperature excursions up to 25°C for up to 72 hours. All temperature excursions of the investigational product must be documented in the investigational product accountability log. Any excursions within the allowable temperature range and conditions should be documented, but the investigational product is still acceptable for use and dispensing to subjects. If any excursions are outside of these conditions, the investigational product should not be used to treat subjects. If this occurs, the individual preparing the investigational product should immediately quarantine the product and report the kit(s) as unacceptable for dispensing to WebEZ to remove it from inventory.

## **12.5. Investigational Product Accountability**

It is the responsibility of the Investigator to ensure that all investigational product received at the site will be inventoried and accounted for throughout the study and the result recorded on the drug accountability form maintained in the Pharmacy Manual. The person responsible for preparing the syringe containing the investigational product will be instructed to return all original containers, whether empty or containing investigational product, when instructed by the study monitor to return. Investigational product returned by the clinical site staff will be stored and disposed of according to the Sponsor's instructions. Investigational product accountability will be verified by the study monitor during the study. Investigational product will be stored in a limited access area or in a locked refrigerator under appropriate environmental conditions.

The Investigator agrees not to supply the investigational product to any person other than sub-Investigators, designated staff and the subjects participating in the study. Investigational product

may not be relabeled or reassigned for use by other subjects except under special circumstances approved by the Sponsor.

The Investigator will retain and store all original containers returned by the clinical site staff until these containers are inventoried by the study monitor. Unless otherwise instructed by the Sponsor, the Investigator agrees at the end of the study to return all original containers, whether empty or containing investigational product, to the Sponsor as instructed by the study manager. The Investigator agrees to neither dispense the investigational product from, nor store it at, any site other than the study sites agreed upon with the Sponsor.

The Sponsor will ensure proper disposal of original containers empty or full of returned or unused investigational product. Appropriate documentation will be maintained. Permission may be granted for local disposal, with supporting documentation.

## **13. ETHICAL ASPECTS**

### **13.1. Investigator Responsibilities**

The Investigator is responsible for ensuring that the clinical study is performed in accordance with the protocol, the Declaration of Helsinki, as well as with the Note for Guidance on Good Clinical Practice (ICH/135/95), and applicable regulatory requirements. These documents set forth that the informed consent of the subjects is an essential precondition for participation in the clinical study.

### **13.2. Institutional Review Board (IRB)**

This study will be undertaken only after full approval of the protocol and addenda has been obtained from a designated IRB and the Sponsor has received a copy of this approval.

The IRB must be informed of all subsequent protocol amendments issued by the Sponsor.

Reports on, and reviews of, the study and its progress will be submitted to the IRB by the Investigator at intervals stipulated in their guidelines.

### **13.3. Informed Consent**

Each subject must give written consent and sign other locally required documents after the nature of the study has been fully explained. The consent form is typically signed at the Screening Visit (Visit 1) and must be completed prior to performance of any study-related activity. The consent form that is used must be approved both by the Sponsor and by the reviewing IRB. The informed consent is in accordance with the Declaration of Helsinki, current International Conference for Harmonisation (ICH) Good Clinical Practice (GCP) guidelines, and Sponsor policy.

The Investigator must explain to potential subjects the aims and methods of the study. The Investigator must also explain potential discomfort, benefits, and risks of study participation. Subjects will be informed that they are free not to participate in the study and that they may withdraw consent to participate at any time. They will be told which alternative treatments are available if they decline to participate in the study. Subjects will also be told that declining to

participate in the study will not prejudice future treatment. Finally, they will be told that their records may be examined by competent authorities and authorized persons, but that personal information will be treated as strictly confidential and will not be publicly available. Subjects must be given the opportunity to ask questions. After this explanation and before entry into the study, consent should be appropriately recorded by means of the subject's dated signature of the informed consent form. If a subject is unable to read, an impartial witness must be present during the entire informed consent discussion. The signature of the impartial witness on the informed consent form will certify the subject's consent. The subject should receive a signed and dated copy of the informed consent form.

## **14. ADMINISTRATIVE REQUIREMENTS**

### **14.1. Protocol Modifications**

All protocol amendments must be issued by the Sponsor, signed and dated by the Investigator, and should not be implemented without prior IRB approval, except where necessary to eliminate immediate hazards to the subjects or when the change(s) involves only logistical or administrative aspects of the study (e.g., change in monitor, change of telephone number). Responsibilities for reporting protocol amendments to any Regulatory Authority (if applicable) and/or IRB are further described in the Ethical Aspects section of the protocol.

In situations requiring a departure from procedures defined in the protocol, the Investigator or other physician in attendance will contact the site manager, Medical Monitor, or other appropriate Sponsor representative by email or telephone (see [Sponsor Contact Information page](#)). If possible, this contact will be made before implementing any departure from protocol. In all cases, contact with the Sponsor must be made as soon as possible to discuss the situation and agree on an appropriate course of action. The eCRF and source document will describe any deviations from procedures defined in the protocol and the circumstances requiring such deviations.

